### 5.7 Safety Analyses

Safety evaluations will be performed using the safety set and analyzed according to the analysis methods described in 5.1.1 unless specified otherwise. Missing values will not be imputed unless stated otherwise.

### 5.7.1 Adverse Events

Adverse events data was collected from the time that first day of treatment for the duration of the trial.

Serious adverse events reported from the time of informed consent up to 4 weeks (28±4 days) after their last administration of study treatment will be recorded as part of the study. A treatment-emergent adverse event (TEAE) is defined as an AE that occurred or increased in severity after the first dose of study medication was taken. AEs occurring or increasing in severity up to 4 weeks (28±4 days) after their last administration of study treatment, will also be classified as treatment-emergent.

A treatment-emergent serious adverse event (TESAE) is defined as a SAE occurring or increasing in severity after the first dose of study medication was taken, and including SAEs occurring up to 4 weeks (28±4 days) after their last administration of study treatment. An AE will be classified as related to study medication if the relationship to study medication was recorded as certain, probable/likely and possible. An AE will be classified as unrelated to study medication if the relationship to study medication was recorded as unlikely and unrelated.

An AE leading to study discontinuation will be defined as an AE where the reason for study withdrawal was recorded as being due to an AE on the Study Termination CRF page and the response to Other Action taken on the Adverse Events CRF page, was recorded as early study termination.

An AE leading to treatment discontinuation is defined as an AE where the action taken with study drug of the event was recorded as drug withdrawn on the 'Adverse Events' CRF page.

Adverse events will be reported on a per-subject basis and per-event. On a per-subject basis this means that even if a subject reported the same event repeatedly (i.e., events mapped to the same PT) during the study period, the event will be counted only once. In the latter case the event will be assigned the worst severity and the strongest relationship to the study medication. The earliest date will be regarded as start date of the event and the latest date/time will be regarded as stop date of the event within the assigned study period.

The relative day of start/stop date of AE will be calculated as follows:

- Start/Stop date of AE date of first study medication administration +1 (if start/stop date of AE is completely known);
- Imputed start/stop date of AE date of first study medication administration +1 (if start/stop date
  of AE is incomplete);
- missing (if start/stop date of AE is unknown).

The duration of an AE will be calculated as follows:

- date of last study medication administration Start date of AE + 1 (when both dates are completely known);
- Date of completion/discontinuation Start date of AE + 1 (when the Start date of AE is fully known but the AE is not resolved at the end of the study): in this case the duration will be presented as ">x days" in the listing rather than "x days";
- missing (when the Start date of AE is incomplete or unknown, or when the AE has resolved but
  with an incomplete or unknown end date, or when the Start date of AE is > date of
  completion/discontinuation and the AE is not resolved).

The overall summary of AEs table will include the counts and percentage of subjects with at least 1 TEAE and the number of events with each of the following, tabulated by overall subjects receiving VIT-2763, subjects receiving VIT-2763 by dose daily frequency and on all subjects receiving placebo within each cohort:

- Any TEAEs
- Any severe TEAEs
- · Any TEAEs related to study medication
- Any severe TEAEs related to study medication
- Any TEAEs leading to treatment discontinuation
- Any TEAEs leading to study discontinuation
- Any serious TEAEs
- Any serious TEAEs related to study medication
- Any TEAEs leading to death (outcome "fatal")
- Any TEAEs leading to death related to study medication

All TEAEs / serious TEAEs / TEAEs related to study medication / serious TEAEs related to study medication / severe TEAEs / moderate TEAEs / mild TEAEs / severe TEAEs related to study medication / TEAEs excluding SAEs (Clinical trial.gov and EudraCT -requirement) / TEAEs leading to treatment discontinuation / TEAEs leading to study discontinuation / TEAEs leading to death will be tabulated by treatment group and overall including the number of subjects, percentage of subject with at least 1 TEAE and number of TEAEs by SOC and PT (both sorted alphabetically).

A listing of all AEs, all SAEs and all AEs leading to death with flag for AE onset outside of the ontreatment period will be provided including relative day and duration of AE.

A listing of TEAEs leading to treatment discontinuation and dose interruption will be also computed.

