10.5 Recording and Reporting

10.5.1 Persistent or Recurrent AEs

AEs that extend continuously, without resolution, between trial assessments should only be recorded once in the eCRF. The initial severity of the event should be recorded, and the severity should be updated to reflect the most extreme severity any time the event worsens.

AEs that resolve and subsequently recur should have each recurrence recorded separately in the eCRF.

All AEs persisting at the time of study completion will be followed by the Investigator through contact with the subject until resolution or stabilisation, or the subject is lost to follow-up and cannot be contacted. The outcome must be documented in the subject's source documents.

10.5.2 **Diagnosis Versus Signs and Symptoms**

Where possible, the Investigator should report a diagnosis rather than individual signs and symptoms or abnormal laboratory values. However, if a constellation of signs and/or symptoms cannot be medically characterised as a single diagnosis or syndrome at the time of reporting, each individual event should be recorded in the eCRF. If a diagnosis is subsequently established, all previously reported AEs based on signs and symptoms should be nullified and replaced by 1 AE report based on the single diagnosis, with a starting date that corresponds to the starting date of the first symptom of the eventual diagnosis.

The Investigator should use standard medical terminology/concepts; avoid colloquialisms and abbreviations. Only 1 AE term should be recorded in each event field in the eCRF.

Pre-existing Medical Conditions 10.5.3

A pre-existing medical condition is one that is present at the screening visit for this study. Such conditions should be recorded on the medical history eCRF. A pre-existing medical condition should be recorded as an AE only if the frequency, severity, or character of the condition worsens during the study. When recording such events on the AE eCRF, it is important to convey the concept that the pre-existing condition has changed by including applicable descriptors (e.g., "more frequent headaches").

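### For a repeated AE term, SAP 5.7.1 takes the worst severity and the strongest relationship separately, so a subject can be counted with a severe related TEAE that no single event shows

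*SAP*

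**What the plan says.** SAP 5.7.1 sets the reporting units: "Adverse events will be reported on a per-subject basis and per-event". For the per-subject count, the rule is as follows: "even if a subject reported the same event repeatedly (i.e., events mapped to the same PT) during the study period, the event will be counted", with the count limited to one. The attributes of that single event come next: "In the latter case the event will be assigned the worst severity and the strongest relationship to the study medication". A further sentence takes its start from the earliest occurrence and its stop from the latest, so the text describes one merged event per subject and term.

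Relatedness is dichotomised in the same section: "An AE will be classified as related to study medication if the relationship to study medication was recorded as certain, probable/likely and possible". Unlikely and unrelated form the other class.

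Two planned outputs cross severity with relationship. The overall summary has the row "Any severe TEAEs related to study medication". The SOC/PT tables include "severe TEAEs / moderate TEAEs / mild TEAEs / severe TEAEs related to study medication", each reported "including the number of subjects, percentage of subject with at least 1 TEAE and number of TEAEs by SOC and PT". Neither document gives a separate derivation for these crossed outputs.

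On data capture, protocol 10.5.1 states: "AEs that resolve and subsequently recur should have each recurrence recorded separately in the eCRF". Protocol 10.4.2 has the investigator judge causality for each AE.

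**The concern.** A maximum over severity and a maximum over relationship are each sensible alone, because the value reported did occur in some record. Used together they can describe an event that never occurred: the severity comes from one episode and the relationship from another. Because each recurrence has its own record and its own causality judgement, the two maxima can come from different episodes.

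The severe related count is among the first figures a reader of a small safety study looks at. The study is descriptive throughout (SAP 3.2), so no test or interval tempers it: the count is the result. A false case in an active arm suggests a drug effect that no investigator reported, and one in placebo could hide a real imbalance. SAP 5.1.8 also repeats the overall summary by body weight, gender and race, so the row appears again with smaller denominators.

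**Working it through.** The plan states no figure for this point, so there is nothing to reproduce. The check compares two ways of counting.

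**Inputs**
- Severity: mild, moderate, severe (protocol 10.4.1).
- Relationship: five levels, three classed as related and two as unrelated (protocol 10.4.2, SAP 5.7.1).
- Arm sizes for QD : BID : placebo: 8:8:4 in Cohort I (at least 20 subjects) and 4:4:2 in Cohort II (up to 10), from protocol 12.3.

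**Worked case**

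| Headache record | Severity | Relationship | Severe and related? |
|---|---|---|---|
| 1 | severe | unrelated | no |
| 2 | mild | possible | no |
| Merged under SAP 5.7.1 | severe | possible (related) | yes |

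If the row is filled from the merged event, the subject count is 1. The event count beside it, taken from the records, is 0.

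**How general this is.** Let k be the number of occurrences of one term in one subject, r the number of relationship levels, and u the number of those classed as unrelated. The number of ordered combinations is N = (3r)^k.
- Merged rule (any record severe, any record related): N − (2r)^k − (3u)^k + (2u)^k.
- Same-record rule (one record both severe and related): N − (2r + u)^k.

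| k | r, u | N | Merged rule | Same-record rule | False |
|---|---|---|---|---|---|
| 1 | 2, 1 | 6 | 6 − 4 − 3 + 2 = 1 | 6 − 5 = 1 | 0 |
| 2 | 2, 1 | 36 | 36 − 16 − 9 + 4 = 15 | 36 − 25 = 11 | 4 |
| 2 | 5, 2 | 225 | 225 − 100 − 36 + 16 = 105 | 225 − 144 = 81 | 24 |
| 3 | 2, 1 | 216 | 216 − 64 − 27 + 8 = 133 | 216 − 125 = 91 | 42 |

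These are counts of combinations, not probabilities. They show that the error needs a repeated term (k = 1 gives none). They also fix its direction: any subject the same-record rule counts is also counted by the merged rule, so the merged rule never misses a true case and can only over-count.

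**Weight of one false subject**
- Cohort I at its minimum: 1/8 = 12.5% of an active arm, 1/4 = 25% of placebo, 1/16 = 6.25% of all VIT-2763 subjects.
- Cohort II at its maximum: 1/4 = 25% of an active arm, 1/2 = 50% of placebo.

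**Imputation.** SAP 5.1.9 sets missing severity to severe and missing causality to related. An imputed attribute on one record can therefore combine with a recorded attribute on another.

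**The case against.** The strongest reply is that the SAP does not prescribe an order of steps. It classifies relatedness for each AE, and it describes the summary rows as subjects with at least one TEAE in the category, with event counts alongside. On that reading a programmer selects the severe related records first and then counts subjects, the artefact does not arise, and a row cannot show one subject and no events. This reading is plausible. However, the SAP does not state it, and its only explicit per-subject rule builds the merged event. A plan should not rely on the programmer departing from its stated rule.

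Other points stand and limit the concern:
- The percentages are simply one subject's weight in a small arm, and Cohort I may exceed 20. The documents give no rate for discordant repeats. In the Phase 1 study all TEAEs were mild or moderate (protocol 1.2.3), though that was in healthy subjects with at most 7 days of dosing.
- Any error is in the cautious direction, and record-level values remain in the AE listing and the event counts.
- Protocol 12.8.1 asks for tables by severity and by relationship, and its summary list has no severe related row. The crossed outputs are additions in the SAP.

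Two stronger readings may tempt a reader. One is that a serious but unrelated event inherits a related label from a non-serious occurrence. The documents do not support this: the sentence assigns severity and relationship only, and no rule carries seriousness across occurrences. The other is that the primary safety tables are generally distorted. They are not, because by-severity and by-relationship tables each report a value that really occurred.

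**Conclusion.** The concern holds within narrow limits. As written, the SAP 5.7.1 rule can place a subject in the severe related category when no single event qualifies. It affects the subject counts in one overall-summary row, including its subgroup repeats, and in one SOC/PT table.

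The conclusion rests on two conditions: that the crossed outputs are derived from the merged event, and that some subject has at least two treatment-emergent occurrences of the same preferred term, one severe but unrelated and another related but not severe. Discordance between different preferred terms does not trigger it. If both conditions are met, each such subject adds 12.5 percentage points to an active arm or 25 to placebo at the Cohort I minimum size. How likely that is cannot be estimated from the documents. The defect is small and traceable, but it comes from a stated rule that gives a wrong count, so it is worth correcting.

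**What to change.** Add to SAP 5.7.1 that any category crossing severity with relationship is derived on individual event records before collapsing to subject and preferred term, so that a subject counts only if at least one single event meets both conditions. In the same place, limit the worst-severity maximum to the severity-only tables and the strongest-relationship maximum to the relationship-only tables.

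In the worked case the subject count becomes 0 and agrees with the event count. A simple programming check follows: every subject counted in the severe related row must have at least one listed event that is both severe and related, after any imputation.

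The cost is about one sentence in the SAP and confirmation of the order of two derivation steps. Data collection does not change, the one-way tables stay as they are, and no true severe related case is lost.

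### The SAP measures AE duration to the last dose instead of the AE stop date, so resolved events get wrong durations, zero or negative if they begin after dosing ends

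*SAP*

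**What the plan says.** SAP 5.7.1 gives three rules for the duration of an AE.

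1. With complete dates: "date of last study medication administration Start date of AE + 1 (when both dates are completely known".
2. For events in the situation "when the Start date of AE is fully known but the AE is not resolved at the end of the study": completion or discontinuation date minus start date plus 1, shown as a lower bound.
3. Missing in several cases. One is a resolved event "with an incomplete or unknown end date". Another is an unresolved event that starts after completion or discontinuation.

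The listings of all AEs, all SAEs and fatal AEs "will be provided including relative day and duration of AE".

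The same section uses AE stop dates elsewhere. When events are collapsed within a subject, "the latest date/time will be regarded as stop date of the event". It also classes as treatment-emergent "AEs occurring or increasing in severity up to 4 weeks (28±4 days) after their last administration of study treatment".

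For relative day, 5.7.1 uses "Start/Stop date of AE date of first study medication administration +1" without distinguishing events before the first dose from events after it. SAP 5.1.2 does distinguish them: a date before the first dose is a plain difference, and 1 is added only from the first dosing day onward.

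**The concern.** A resolved AE with complete start and stop dates can fall only under rule 1, and rule 1 never uses the stop date. It therefore measures the time from onset to the end of dosing, not how long the event lasted. Rule 3 shows that the end date was intended as an input, so the list is inconsistent with itself.

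Events that begin after the last dose are in scope, because the treatment-emergent window runs 28±4 days beyond it and Protocol 10.2 collects AEs to Week 16. For resolved events in that window the formula gives impossible values.

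The trial plans about 36 randomised subjects and only descriptive analyses. Individual listings will therefore carry much of the safety reading. In the duration column, brief early events would look longest, and late persistent ones would look short.

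**Working it through.** **Inputs**
- Rule 1, SAP 5.7.1. The minus sign is absent from the extracted text, as it is in the neighbouring formulas; subtraction is the only sensible reading.
- Last dose L = Day 84 for a completer, from the 84-day treatment period in SAP 1.1.
- Treatment-emergent window to 28 + 4 = 32 days after last dose, SAP 5.7.1, so to 84 + 32 = Day 116.

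The plan states no numerical figure to reproduce, so the check compares the two formulas.

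**Formulas**, for an event starting on day S and stopping on day E:
- SAP: L − S + 1
- Duration from the event's own dates: E − S + 1
- Error: (L − S + 1) − (E − S + 1) = L − E

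The error is zero only when E = L. Events that stop before the last dose are overstated, and events that stop after it are understated.

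| AE start to stop | SAP formula | Actual duration |
|---|---|---|
| Day 10 to 12 | 84 − 10 + 1 = 75 | 12 − 10 + 1 = 3 |
| Day 80 to 100 | 84 − 80 + 1 = 5 | 100 − 80 + 1 = 21 |
| Day 84 to 84 | 84 − 84 + 1 = 1 | 84 − 84 + 1 = 1 |
| Day 85 to 87 | 84 − 85 + 1 = 0 | 87 − 85 + 1 = 3 |
| Day 95 to 97 | 84 − 95 + 1 = −10 | 97 − 95 + 1 = 3 |
| Day 112 to 112 | 84 − 112 + 1 = −27 | 112 − 112 + 1 = 1 |
| Day 116 to 116 | 84 − 116 + 1 = −31 | 116 − 116 + 1 = 1 |

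**Onset after last dose.** If onset is k days after the last dose, the formula gives 1 − k. That is 0 or less for every k ≥ 1, whatever the last-dose date. All 32 possible onset days from Day 85 to Day 116 are affected.

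**Could another section rescue the rule?** SAP 5.1.9 uses the last-dose date when imputing missing AE stop dates, but limits that imputation to treatment emergence and timing relative to first dose. It does not redefine duration. Protocol 12.8.1 gives no duration formula.

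**Gaps between the rules.** Read literally, the two dates in rule 1 are last dose and AE start. An unresolved event can satisfy that condition as well, so rules 1 and 2 overlap. A subject who was never dosed has no last-dose date, so a resolved event with complete dates in that subject fits none of the three rules.

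**Relative day.** For an AE on the day before first dose, the date difference is −1. SAP 5.7.1 gives −1 + 1 = Day 0; SAP 5.1.2 gives Day −1. The case can arise, because Protocol 10.2 starts AE reporting at consent and Protocol 12.8.1 has pre-dose events listed.

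**The case against.** The strongest reply is that little depends on this column. The primary AE endpoints are events by system organ class, preferred term, severity and relationship; duration is not among them. The overall AE summary, the tables by class and term, the treatment-emergent definition, the discontinuation flags and the subgroup outputs do not use it. No inferential comparison is planned. SAP 5.1.5 has the listings show all CRF data, so a reader should be able to recover the true duration from the start and stop dates. The slip also reveals itself: the two dates in rule 1 were most plausibly meant to be AE start and stop, and negative values would alert a programmer. Unresolved events that begin after the last dose have their own rule. The relative-day conflict shifts a label by one day, for pre-dose events that are listed and not tabulated.

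The points on scope stand. The effect is limited to derived values in listings, the zero or negative durations concern resolved events provided rule 2 takes precedence for unresolved ones, and the relative-day point is minor. None of this makes rule 1 correct. A reader's ability to recalculate a wrong value is not a reason to report it, and relying on a programmer to depart from the written rule leaves the derivation outside the plan.

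**Conclusion.** The concern holds. As written, duration is wrong for every resolved AE with complete dates unless the event stops on the day of last dose. The error in days equals last-dose date minus AE stop date: +72 for the Day 10 to 12 event (75 against 3) and −13 for the Day 95 to 97 event (−10 against 3). Resolved events that begin after the last dose always get zero or a negative number. The conflict over relative day is real but small.

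The worked figures assume a last dose on Day 84; the pattern does not depend on that day. The conclusion rests on reading the missing operator as a minus sign. In the visible text the consequences stop at the AE, SAE and fatal-AE listings, and the primary-endpoint counts and percentages do not change. The rule should be corrected because it puts wrong safety values into required outputs and costs almost nothing to mend.

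**What to change.** Replace rule 1 in SAP 5.7.1 with: *stop date of AE − start date of AE + 1, for resolved AEs whose start and stop dates are both complete*. Limiting it to resolved events also removes the overlap with rule 2, and it covers resolved events in subjects who were never dosed. Rules 2 and 3 can stay as they are.

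For AE relative day, refer to the study-day rule in SAP 5.1.2, so that no 1 is added before the first dose. Apply it to start and stop dates, observed or imputed.

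The cost is a few words of SAP text and the matching change to the listing program. No new data are needed, and no table of counts has to be rerun.

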### 5.7.2 Clinical Laboratory Evaluations

A list of all protocol specified clinical laboratory tests are given in Appendix A and will be performed at screening, baseline, week 1, week 2, week 4, week 8 and week 12 for haematology, biochemistry and urinalysis and at screening, baseline, week 4 and week 12 for coagulation in accordance with the Schedule of Events in section 2.3. For analyses, Planned Assessment Windows (see Section 2.2.3) are defined for each visit.

Descriptive statistics will be performed for laboratory parameters on a continuous scale for the scores and change from baseline for each visit split by treatment group.

If multiple tests were performed at baseline, the latest non-missing measurement prior to the first administration of study treatment will be used for the baseline value. For multiple tests at post-baseline visits occurring during the same visit window, the closest measurement will be used for the analyses and summary tables. When two measurements are exactly equidistant to the exact visit date, the later will be used for the analyses and summary tables. Laboratory values expressed as 'less than" or "greater than" will be imputed using the next numerical value (i.e. '<2.00' imputed as 1.99, ">0.3" imputed as 0.4).

Shift tables for the haematology and biochemistry laboratory parameters comparing values low, normal and high using the standard reference ranges will be presented for the baseline laboratory measurement versus the endpoint measurement for each subject. The number and percentage of subjects with abnormal values for each analyte will be summarized at each analysis visit. Abnormal values for each analyte will be determined using normal ranges provided by the central laboratory. The descriptive analysis by visit will also include an overall summary. If any of the subject's post-baseline measurements are abnormal (low or high), then the subject is classified as abnormal in the overall summary.

All laboratory results (local and central values) will be listed, including all unscheduled visits.

Only central laboratory parameters will be analysed.

eGFR formula: 186 x (Creatinine/88.4)-1.154 x (Age)-0.203 x (0.742 if female) x (1.210 if black)

Measurements of Alkaline Phosphatase (ALP) performed before the 1st of December 2020 will be recalibrated before being described with the ones recorded on or after this date. For this, those old measurements will be multiplied by 1.071 to be described with the new calibrated ALP measurements.

